#### **10.0. MISSING OR INCOMPLETE DATA**

For the ITT population, a multiple imputation method will be implemented if the missing data mechanism is at least missing at random (MAR). Meanwhile, for the modified ITT population, analyses with and without imputation will be conducted. For this imputation, the method of Last Observation Carried Forward (LOCF) will be used as a single imputation approach (Elobeid MA et al, 2009). In this approach, if a subject's measurement is missing at a post-randomization visit, the value from the most proximal prior visit will be used for all missing visits afterwards. The imputation methods will only be applied to body weight. No imputations will be performed for other variables.

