8.1. Sample Size

A standard deviation of 15.0 lb for change in body weight over 16 weeks was derived from the largest variability observed in a previous study by Davis et al. (2010) that compared weight loss over 16 weeks on the Mcdifast 5 & I Plan@ (-29.8 \pm 13.0 lb) vs. a food-based isocaloric control diet (-14.3 \pm 15.0 lb). Using this estimate of expected variability and accounting for a more conservative mean difference in weight loss between groups over a similar timefi'ame, an evaluable sample of 55 participants in each group (165 total) will provide 80% power to detect a difference of 9.0 pounds (an effect sized of 0.60). This assumes a nominal a = 0.025 (two-sided) accounting for two primary comparisons, each Medifast group compared to the control group, in order to maintain an overall type I error of a = 0.05. To account for possible attrition, a total sample of 198 participants (n = 66 *I* group) will be randomized.

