8.2.2. Outcome Analysis

Descriptive statistics [number of participants, mean, standard error of the mean (SEM), standard deviation, median, interquartile limits, minimum and maximum] will be presented for continuous variables. Ratings for categorical variables will be presented as counts and percentages.

Baseline comparisons for demographic characteristics between control and active groups will be completed with the Chi-Square test, Fisher's exact (two-tail) tests, or analysis ofvariance (ANOVA), as appropriate.

A mixed model repeated measures analysis of covariance (ANCOVA) will be used to assess differences between study groups in continuous outcome variables. Initial ANCOVA models will contain terms for intervention, week, intervention by week interaction, and sex, with baseline measures (where applicable) as covariates. Models will be reduced using a backward selection method until only significant terms and/or intervention and baseline measures (where applicable) remain in the model. Pairwise comparisons between groups at each post-randomization visit will be conducted from the final ANCOVA model, with Dunnett's correction for multiple comparisons between each Medifast group vs. control. Assumptions of normality of residuals will be investigated for each response measurement. If the normality assumption is rejected at the I% level with the Shapiro-Wilk test (Shapiro 1965), then an analysis using ranks or other transformation will be performed.

Counts and percentages of participants who experience weight loss of :0:5% or :0:10% between baseline and each post-randomization visit will be presented. Differences between control and each active group participants with weight loss :0:5% or :0:10% will be assessed using a generalized linear model with a logit link and binomial distribution specified. Initial repeated measures models will contain terms for intervention, week, intervention by week interaction, and sex. Models will be reduced using a backward selection method until only significant terms or intervention remains **in** the model. Pairwise comparisons at each post-randomization visit will be conducted using Dunnett's correction for multiple comparisons between each Medifast group vs. control.

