### **3.0. SIZE OF TRIAL POPULATION**

A standard deviation of 15.0 lb for change in body weight over 16 weeks was derived from the largest variability observed in a previous study by Davis et al. (2010) that compared weight loss over 16 weeks on the Medifast 5 & 1 Plan® (-29.8 ± 13.0 lb) vs. a food-based isocaloric control diet (-14.3 ± 15.0 lb). Using this estimate of expected variability and accounting for a more conservative mean difference in weight loss between groups over a similar timeframe, an evaluable sample of 55 participants in each group (165 total) will provide 80% power to detect a difference of 9.0 pounds (an effect size  $d$  of 0.60). This assumes a nominal  $\alpha = 0.025$  (two-sided) accounting for two primary comparisons, each Medifast group compared to the control group, in order to maintain an overall type I error of  $\alpha = 0.05$ . To account for possible attrition, a total sample of 198 participants will be randomized.

Subjects will be randomized to one of three groups (1:1:1 ratio) stratified by sex to ensure each group is allocated a maximum of 25% male participants. Additionally, the total study sample will be limited to  $\leq 10\%$  of participants with a BMI between  $\geq 27.0$  and  $< 30.0$  kg/m^2, but randomization will not be stratified by BMI.

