### Population(s)

	Table 1	Subject Disposition
ITT	Table 2.1	Demographic Characteristics
ITT	Table 2.2	Vitals
ITT, mITT, Completers	Table 3	Primary Outcome Variable: Body Weight (Visit 7)
ITT, mITT, Completers	Table 4.1	Secondary Outcome Variables: Body Weight (Visits 3, 4, 5, 6)
ITT, mITT, Completers	Table 4.2	Secondary Outcome Variables: Weight Loss $\geq$ 5% and $\geq$ 10%
mITT, Completers	Table 4.3	Secondary Outcome Variables: Body Composition
mITT, Completers	Table 4.4	Secondary Outcome Variables: Body Circumference Parameters
mITT, Completers	Table 4.5	Secondary Outcome Variables: hs-CRP
mITT, Completers	Table 4.6	Secondary Outcome Variable: IWQOL-Lite Questionnaire Outcomes
mITT, Completers	Table 4.7	Secondary Outcome Variable: RAND Health Survey Questionnaire Outcomes
mITT, Completers	Table 4.8.1	Secondary Outcome Variables: Satisfaction and Health/Well-being Questionnaire
mITT, Completers	Table 4.8.2	Secondary Outcome Variables: Satisfaction and Health/Well-being Questionnaire (Recoded)
mITT, Completers	Table 4.9	Secondary Outcome Variables: Program Questionnaire

mITT, Completers	Table 4.10	Secondary Outcome Variable: Weight Loss Program Adherence
mITT, Completers	Table 4.11	Secondary Outcome Variable: Nutrition Support Contact
mITT	Table 5	Summary of Subjects with at Least One Intervention-Emergent Adverse Event

**Note: Tables 3, 4.1, and 4.2 will be generated for Completers, ITT population with multiple imputation applied for the missing data and for the mITT population, both with and without imputation. For the mITT population with imputation, LOCF imputation method applied for missing data will be reflected in footnotes of relevant tables. All other tables generated for the mITT population will be without imputation.**

Table 1  
Subject Disposition

---

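### LOCF for missing mITT body weights biases the week-16 difference, in a direction that depends on dropout and loss in both arms, and no weight analysis is named primary

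*SAP*

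**What the plan says.** The primary outcome is absolute and percent change in body weight from baseline to week 16 (SAP 8.1). Weight is measured at weeks 2, 4, 8, 12 and 16. For mITT participants with a missing weight, SAP 10.0 states that "the value from the most proximal prior visit will be used for all missing visits afterwards". This is a single imputation and applies to body weight only.

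The note under SAP 16.0 carries it into the tables: "For the mITT population with imputation, LOCF imputation method applied for missing data" is to be shown in footnotes. Tables 3, 4.1 and 4.2 are produced four ways: Completers, ITT with multiple imputation, mITT with LOCF, and mITT without imputation. Neither document names one of these as primary or calls LOCF a sensitivity analysis. The multiple imputation is conditional on the data being at least missing at random.

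Protocol 8.2.2 had planned a longitudinal model: "A mixed model repeated measures analysis of covariance (ANCOVA) will be used to assess differences between study groups in continuous outcome variables". SAP 9.0 instead uses ANCOVA at each visit, and SAP 14.0 does not list that change. Protocol 8.2.4 did allow LOCF as one option. Protocol 6.7 and 10.5 provide for an attempted week-16 visit for participants who withdraw.

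**The concern.** A participant last seen at week 2 or 4 has reached only part of the 16-week loss. LOCF enters that part as if it were the final result. Each arm's mean loss is then too small by an amount that grows with its dropout and with its loss, and the two shortfalls cancel only by coincidence. Filled values are also treated as observed.

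With the SAP's visit-wise ANCOVA, mITT without imputation drops anyone who lacks a week-16 weight. The mITT tables therefore offer either complete cases or LOCF, and no longer a likelihood analysis that uses every observed weight. If the condition on the multiple imputation is judged not to hold, LOCF is the only imputed weight result left. Because the four results are unranked, any of them could be reported as the main finding.

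**Working it through.** **1. The plan's own figure.** SAP 3.0 gives "A standard deviation of 15.0 lb for change in body weight over 16 weeks" and says the sample "will provide 80% power to detect a difference of 9.0 pounds"; Protocol 8.1 adds "This assumes a nominal a = 0.025 (two-sided) accounting for two primary comparisons". The effect size is 9.0/15.0 = 0.60. Noncentral-t power is 79.9% at 54 per group and 80.7% at 55, so the stated 55 is reproduced. The 198 randomized against 165 evaluable imply attrition of 1 - 165/198 = 16.7%. No rate by arm is given.

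**2. Inputs.**
- Control mean loss MC = 14.3 lb, from the planning study's "food-based isocaloric control diet (-14.3 ± 15.0 lb".
- Active mean loss MT = 14.3 + 9.0 = 23.3 lb at the planned difference.
- Assumed: last visits spread evenly over weeks 2, 4, 8 and 12; dropouts would have followed their arm's curve; no week-16 retrieval.

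**3. Share of loss not yet reached (g).** Linear loss: (14/16 + 12/16 + 8/16 + 4/16)/4 = 0.594. Two increasingly decelerating curves give 0.45 and 0.33.

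**4. Bias.** With p as dropout, LOCF reduces each arm's mean loss by g × p × M. The bias in the difference (active minus Control loss) is therefore g × (pC × MC - pT × MT).

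| Dropout Control / active | pC×MC - pT×MT (lb) | Bias at g = 0.594 / 0.33 (lb) | LOCF shows (true 9.0 lb) |
|---|---|---|---|
| 16.7% / 16.7% | -1.50 | -0.89 / -0.50 | 8.1-8.5 |
| 25% / 8.3% | 3.58 - 1.94 = +1.63 | +0.97 / +0.54 | 9.5-10.0 |
| 8.3% / 25% | 1.19 - 5.83 = -4.63 | -2.75 / -1.53 | 6.2-7.5 |

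**5. Direction.** The bias is zero when pC/pT = MT/MC = 23.3/14.3 = 1.63. Below that ratio it is toward the null. At 20% / 14%, for example: 0.594 × (2.86 - 3.26) = -0.24 lb, although Control drops out more.

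**6. No true difference.** With both arms losing 14.3 lb and 25% / 8.3% dropout, the spurious difference is g × 14.3 × 0.167: 1.4 lb at g = 0.594 and 0.8 lb at g = 0.33. Equal dropout gives zero. With linear loss, 66 per arm and SD 15, simulated rejection at nominal 0.025 is about 0.05-0.06. At 20% / 14% it is only about 0.027. With a decelerating curve (800 trials per scenario) it was 0.030 at 25% / 8.3% and 0.046 at the reverse, against 0.015 and 0.028 for multiple imputation in the same trials.

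**7. Precision and power (800 trials per scenario, SD 15).** LOCF standard errors were 3-11% below those of multiple imputation; at linear loss, 9 lb and 25% / 8.3%, they were 2.56 against 2.70. With 8.3% / 25% dropout and a 9 lb effect, coverage of the 97.5% interval fell to 0.86 (linear) or 0.91 (decelerating), and power fell from about 0.88 to 0.51 or 0.67. Multiple imputation bias was about 0.2 lb or less, in line with the full data.

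**The case against.** Several points on the other side stand.

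- **LOCF is not alone.** It is footnoted as LOCF and sits beside multiple imputation, and the protocol had listed it as an option. Part of the harm comes from the unnamed primary analysis, and naming one would cure that part.
- **The inputs are assumed.** A threefold dropout gap is not in the documents. Control completers become eligible for study food, which is a reason to stay; the lack of support after one session is a reason to leave. The direction cannot be predicted.
- **Week-16 visits for withdrawals** would shrink the bias. They are only attempted, so they reduce it without removing it.
- **The standard-error shortfall is modest.** The LOCF standard error roughly matches the sampling spread of the LOCF quantity itself. Bias is the larger problem.
- **A mixed model and the planned imputation both assume missing at random.** Deleting LOCF without a replacement sensitivity analysis would leave nothing that departs from that assumption. If dropouts regain weight, LOCF overstates their loss instead.

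A reader might infer that any excess of Control dropout favours the sponsor's programs, or that LOCF is harmless when dropout is equal. Step 5 and the first row of the table show that neither follows when there is a real effect. A reader might also infer worse null behaviour. A spurious 1.7 lb needs a 20-point gap (0.594 × 14.3 × 0.20), and a rejection rate near 0.08 was reached only with an SD of 10 lb. The documents give SDs of 13.0 and 15.0 lb.

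**Conclusion.** The point holds. LOCF does not estimate the week-16 difference that the trial is designed to measure, and it cannot be defended as reliably conservative. At the planned 9.0 lb effect the distortion runs from about +1.0 lb to -2.8 lb over the dropout patterns examined. It is toward the null unless Control dropout exceeds about 1.6 times active dropout. With no true effect, a large Control excess creates 0.8-1.4 lb and roughly doubles the nominal error rate under linear loss.

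These sizes rest on assumed dropout rates, timing and curve shape, with dropouts placed on their arm's curve and no retrieved weights. The mechanism needs only that weight keeps falling after the last visit. The documents do not support reading LOCF as the declared primary analysis or as a choice that systematically favours the programs.

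**What to change.** In SAP 10.0 and Tables 3, 4.1 and 4.2:

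1. Replace LOCF for mITT weight with a repeated-measures mixed model in the spirit of Protocol 8.2.2. Fix the terms as intervention, week, intervention by week, sex and baseline, with unstructured covariance, and take the week-16 contrast. Do not carry over the protocol's backward selection, which can remove intervention by week; the protocol also names no covariance structure.
2. Name this model or the planned multiple imputation as the primary analysis.
3. Derive 5% and 10% responder status for missing weights from the multiple imputation.
4. State that retrieved week-16 weights are used where available.
5. Add a multiple-imputation sensitivity analysis that departs from missing at random, for example with dropouts shifted toward baseline weight.
6. If LOCF is kept at all, label it sensitivity only.

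The cost is SAP wording, some extra analysis work and one replaced set of tables. Comparability with older weight-loss reports that used LOCF is reduced.

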#### **11.0. SAFETY ANALYSIS**

Safety assessments will be determined from intervention-emergent AEs that occur after randomization at Visit 2 (week 0). Possible differences in the number of participants with at least one AE will be assessed with Chi-Square or Fisher's exact test.

Participants who achieve a BMI of  $19.0 \text{ kg/m}^2$  or below will discontinue the weight loss diet and begin a maintenance diet and will be asked to return for remaining clinic visits. These participants will be noted in the safety analysis.

Vitals (blood pressure, pulse rate) will be summarized by group with descriptive statistics.

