At Visit 6 (week 12), participants will arrive at the clinic fasted $(12 \pm 2 \text{ h})$, water only, anchored to time of gown body weight measurement) to undergo clinic visit procedures (evaluations of inclusion/exclusion criteria, concomitant medication/supplement use, vital signs, and AEs). Gown body weight and body circumferences [waist, hip, chest, upper arm (dominant arm), and thigh (dominant leg)] will be measured. Additionally, female participants <60 years of age will undergo an in-clinic urine pregnancy test. A DXA scan will be performed (female participants <60 years of age must have a negative pregnancy test before the DXA scan is initiated). All participants will then be administered the Program Questionnaire, and TSFL and MEDD participants will place an order for the following four weeks' worth of study foods.

At Visit 7 (week 16), participants will arrive at the clinic fasted $(12 \pm 2 \text{ h}, \text{water only}, \text{anchored}$ to time of gown body weight measurement) to undergo clinic visit procedures (evaluations of inclusion/exclusion criteria, concomitant medication/supplement use, vital signs, and AEs). Blood samples will be collected for analysis ofhs-CRP, with additional blood samples collected and archived for possible future analysis of non-genetic indicators of inflammation and metabolism. Gown body weight and body circumferences [waist, hip, chest, upper arm (dominant arm), and thigh (dominant leg)] will be measured. Additionally, female participants <60 years of age will undergo an in-clinic urine pregnancy test. A DXA scan will be performed (female participants <60 years of age must have a negative pregnancy test before the DXA scan is initiated). Participants will then be administered the IWQOL-Lite, the RAND-36, the Program Questionnaire, and the Satisfaction and Health/Well-being Questionnaire (Appendices 3, 4, 5, and 6). All study participants will be dispensed maintenance handouts and guides prior to discharge from the clinic (see Supplementary Materials). Additionally, eligible Control group participants will be given instructions for placing orders for study food upon completion of all study visits.

					-				
·		ening/ eline	Clinic Visits						
lvisit'	1	2	3	4	5	6	7		
Week	-1	0	2	4	8	12	16		
Infon; ed Consent/I-iiPAA ²	X								
Demographics/Medical History	X								
Clinic Visit'	X	X	Х	Х	X	X	X		
Gown Body Weight	X	Х	Х	Х	X	X	Х		
Anthropometries'		Х		Х	X	X	X		
In-clinic Urine Pregnancy T st ⁵	X	Х		Х	X	X	Х		

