 12 AII three groups will receive diet instructions at Visit 2 (week 0). See Section 6.4.1 for details. JJAII three groups will receive educational materials at Visit 2 (week 0). See Section 6.4.1 for details.

¹⁴The TSFL group and the MEDD group will receive study food as part of the study program. See Section 6.4.1 for details.

¹⁵The TSFL group and the MEDD group will place orders for additional study foods with the study staff at visits 2, 4, 5, and 6 (weeks 0, 4, 8, and 12); these will be shipped directly from Medifast. Orders must be submitted on the visit days. Participants who are assigned to the Control group and complete all study visits will be provided instructions for placing orders for study food at Visit 7 (week 16). "Appendix 5.

¹⁷All study groups will receive handouts with guidance for weight maintenance.

¹⁸Appendix 6.

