'At Visit 2 (week 0), participants will receive a SuperTracker Profile, SuperTracker handouts, and meal plan handouts specific to their targeted calorie level (see Supplementary Materials). Participants will be instructed to set up and use the Super Tracker profile at home. At Visit 7 (week 16), participants will receive maintenance handouts and guides tailored to this control group (see Supplementary Materials). bThe instruction session will be conducted in-clinic by a trained study staff member in a one-on-one format.

'Participants who are assigned to the control group and complete all study visits are eligible to receive study food and will receive instructions on how to place orders at Visit 7 (week 16).

Take Shape For Life Group: The TSFL Program group will be assigned to the Optimal Weight 5 & I Plan'M for weight loss. This is a portion-controlled, nutritionally balanced, low calorie weight loss meal plan (800-1 000 kcal/day) that consists of five Medifast meal replacements, one lean and green meal, and one optional snack each day. The Medifast meal replacements are nutrient dense and fortified with 24 vitamins and minerals to ensure adequate micronutrient nutrition while on a calorie restricted meal plan. All Medifast meal replacements share a similar nutritional profile, allowing them to be used interchangeably. All Medifast meal replacements required for the meal plan will be provided to the TSFL Group participants throughout the 16-week weight loss period of the study. The lean and green meal is a self-prepared meal consisting of a specified amount of lean protein, non-starchy vegetables, and healthy fats. Participants will purchase and prepare foods used for the lean and green meals on their own. Additionally, the Medifast Flavors of Home@ products offer a "heat and serve" alternative to the self-prepared lean and green meal for occasional use. TSFL participants will receive a list of self-selected foods (purchased by the participants) that can be used for the

Confidential

optional snack. In addition, participants will also be provided with up to two boxes (i.e., 14 individual packets) of Medifasl snacks which can serve as a portable, pre-portioned, ready-to-eat alternate snack option.

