9.2.5. Electronic CRF Recording of Adverse Events

All AEs will be recorded on the AE eCRF page. For participants who have an ongoing AE at their final study visit, a follow-up AE eCRF page will be collected after 30 d. Participants will be instructed to notify Biofortis Innovation Services immediately should new AEs emerge for an additional 30 d following their last day on the study diet. All SAEs must be recorded on the AE and SAE eCRF page.

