9.2.6. Serious Adverse Event Follow-Up

For all SAEs occurring during the study or within 30 d of the study diet, the Clinical Investigator must submit follow-up reports to Biofortis Innovation Services regarding the participant's subsequent course. All SAEs that are ongoing at the end of the study or upon discontinuation of the participant's participation must be followed until either:

- The event resolves, or
- The event/condition has stabilized (e.g., in the case of persistent impairment), or
- The event returns to baseline, if a baseline value is available, or
- The participant dies, or
- The event can be attributed to other than the study treatment, or to other than the study conduct.

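### Adverse events in Control participants who order Medifast food after week 16 can be counted in the Control column of Table 5, because the adverse event analysis has no end date

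*SAP*

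**What the plan says.** - **Analysis rule.** SAP 11.0: "Safety assessments will be determined from intervention-emergent AEs that occur after randomization at Visit 2 (week 0"). Protocol 8.2.3 has the same sentence. There is a start date but no end date, and the term intervention-emergent is not defined.
- **Reporting after the diet.** Protocol 9.2.5 asks participants to notify the research organization "should new AEs emerge for an additional 30 d following their last day on the study diet", and adds that "All AEs will be recorded on the AE eCRF page". Protocol 9.2.6 sets the scope of serious AE follow-up as "For all SAEs occurring during the study or within 30 d of the study diet".
- **Control and study food.** Protocol 6.1: "eligible Control group participants will be given instructions for placing orders for study food upon completion of all study visits". The Control footnotes in protocol 6.4.1 make completers eligible to receive the food, with ordering instructions at Visit 7. Protocol 6.4.2 says food after the starter kit is home-delivered.
- **Active arms.** TSFL and MEDD place their last order at week 12 and receive maintenance materials at week 16 (protocol 6.2 footnotes and 6.4.1).
- **Output.** SAP Table 5 shows participants with at least one AE by randomized arm, with p-values. It does not separate the 16-week diet phase from the 30 days after it, and it is the only planned between-arm AE comparison.

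**The concern.** Together these provisions leave a period after week 16 in which three things hold at once: AEs are still collected, a Control participant may be eating the comparator's food, and no rule excludes or separates the resulting events. If Medifast food raises the AE rate, such events increase the Control count and narrow the difference that Table 5 is meant to show. The understatement would favor the sponsor's own product.

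The row for treatment-related events has a similar weakness. Most of the causality grades in protocol 9.2.2 are worded in terms of study foods, so a Control event on ordered food could be graded probably or definitely related and appear in Control's related row.

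With no stated end date, two analysts could also build different versions of Table 5 from the same database.

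**Working it through.** The plan states no AE rate, expected excess or AE power, so it has no figure of its own to reproduce. The window and the food supply can be worked out from the documents. The effect on Table 5 can only be illustrated.

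**1. Length of the overlap.** The diet phase is 16 × 7 = 112 days. For completers I take week 16 as the last day on the study diet, so the AE window is 112 + 30 = 142 days. With delivery lag L, a Control participant who orders at once has 30 − L days on Medifast food inside it:
- L = 0: 30 days, 30/142 = 21%.
- L = 10 (an assumption suggested by the 10-day starter kit in protocol 6.4.1): 20 days, 20/142 = 14%.

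**2. Food left in the active arms at week 16** (protocol 6.4.1 footnotes):
- TSFL: 49 + 4 × 140 = 609 meal replacements supplied, 5 × 112 = 560 needed. The surplus is 49, and 49/5 = 9.8 days.
- MEDD: 42 + 4 × 112 = 490 supplied, 4 × 112 = 448 needed. The surplus is 42, and 42/4 = 10.5 days.

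A fully adherent active participant could therefore go on eating Medifast food for about 10 days of the 30.

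**3. Illustration.** Assumptions: constant hazards, Control risk 20% by week 16, and Medifast food multiplies the hazard by 2.
- Control cumulative hazard to day 112: −ln(0.80) = 0.2231, so h = 0.2231/112 = 0.001992 per day.
- Week 16: Control 20.0%; active 1 − exp(−2 × 0.2231) = 36.0%. Difference **16.0 points**.

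In the tail, a Control participant who orders has added hazard h × [L + 2(30 − L)], and one who does not has 30h. An active participant with R days of residual food has h × [2R + (30 − R)]. Partial reporting multiplies the tail hazards by the reporting fraction. For partial uptake, Control survival is averaged over those who order and those who do not.

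| Scenario | Control | Active | Difference (points) |
|---|---|---|---|
| Full uptake and reporting, L = 0, R = 0 | 1 − exp(−0.3427) = 29.0% | 1 − exp(−0.5061) = 39.7% | 10.7 |
| Same, L = 7 | 1 − exp(−0.3287) = 28.0% | 39.7% | 11.7 |
| Full uptake and reporting, L = 10, R = 10 | 1 − exp(−0.3228) = 27.6% | 1 − exp(−0.5260) = 40.9% | 13.3 |
| 50% uptake, 50% reporting, L = 10, R = 10 | 23.1% | 38.5% | 15.4 |
| 25% uptake, 25% reporting, L = 10, R = 10 | 21.4% | 37.3% | 15.9 |
| No Control uptake, full reporting, R = 0 | 1 − exp(−0.2829) = 24.6% | 39.7% | 15.1 |

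The last row shows that part of the loss in the first two rows has nothing to do with Control food. It comes from assuming that active participants return to the Control hazard at week 16.

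**4. Range.** Over Control risks of 10 to 30% and hazard ratios of 1.5 to 3, the difference shrinks by 23 to 40% with full uptake, full reporting, L = 0 to 7 and R = 0. With 50% uptake, 50% reporting and L = R = 10, it shrinks by about 2 to 8%. With a hazard ratio of 1 both arms have the same risk with or without the tail, so the difference stays at zero.

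**The case against.** The documents do not support several stronger readings that a reader might infer.

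- **That Control completers are given Medifast food at week 16.** They receive ordering instructions, must choose to order, and then wait for delivery.
- **That the plan counts these events against Control.** No passage says so. Intervention-emergent could be read as tied to the assigned intervention, and protocol 9.2.2 introduces causality as relatedness to the diet plan administered. The defect is an undefined term and an open window, so the events can be counted; a planned miscount is not shown.
- **That exposure is reversed after week 16.** The active arms may hold about 10 days of food. Nothing in the text requires participants to return it or to stop using it at Visit 7, and the content of the maintenance materials is not in the text.
- **That the AE difference shrinks by 23 to 40%.** That range needs every Control completer to order promptly and every tail event to be reported. Protocol 6.5.1 has staff ask about AEs only at Visits 2 to 7. After that, new events depend on participants coming forward; the 30-day follow-up page is for AEs already ongoing at the final visit.

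AEs are also neither a primary nor a secondary outcome, and the scenario for the related row needs a probable or definite grade as well. These points reduce the likely size and the severity. They do not supply an end date or a rule for Control participants who have started Medifast food, so the gap stands.

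**Conclusion.** The point holds as a low-severity gap in the safety analysis. Under SAP 11.0 and protocol 8.2.3 as written, AEs that arise in Control participants after they start ordered Medifast food can be counted in the Control column of Table 5, which would understate a program-related excess.

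The amount cannot be determined from the documents, which give no AE rate, uptake or reporting rate. At an assumed Control risk of 20% and hazard ratio of 2, the 16.0-point week-16 difference becomes about 11 points at the extreme and about 15 to 16 points with partial uptake and self-report. All of this rests on constant hazards and on the food itself raising AE risk; without such an effect there is no bias. The primary weight analysis is not affected.

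**What to change.** In SAP 11.0, protocol 8.2.3 and the Table 5 footnote, limit the between-arm comparison to AEs with onset from randomization to the participant's Visit 7 date, or to 16 weeks + 3 days (the end of the visit window) if Visit 7 is not attended. List AEs and serious AEs from the following 30 days separately by arm and, for Control, record whether ordered Medifast food had been started before onset.

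The period of AE collection and the follow-up of serious AEs stay as they are. The cost is one sentence in each place, one listing and one eCRF item. The downside is that late events in the active arms move from Table 5 to the listing, where they are still reported but not tested. The change should be made before database lock and before anyone sees AE counts by arm.
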